**Note that in view of this trial:**

- **Injection-site ecchymosis will not be reported as an AE.**
- **The following pregnancy-related symptoms will not be reported as an AE:**
  - **Nausea, vomiting**
  - **Minor vaginal bleeding**
  - **Gradual onset dyspnea**
  - **Fatigue**
  - **Bilateral leg, arm or facial swelling**
  - **Heart burn, weight gain, abdominal distension**

#### **7.4 Recording Instructions**

AEs are to be recorded in the case report forms as specified.

If required on the AE case report forms, the investigator will use the adjectives MILD, MODERATE, or SEVERE to describe the maximum intensity of the AE. For purposes of consistency, these intensity grades are defined as follows:

MILD	Does not interfere with subject's usual function
MODERATE	Interferes to some extent with subject's usual function
SEVERE	Interferes significantly with subject's usual function

A distinction is made between the gravity and the intensity of an AE. **Severe** is a measure of intensity; thus, a **severe** reaction is not necessarily a **serious** reaction. For example, a headache may be severe in intensity, but is not to be classified as serious unless it meets one of the criteria for serious events listed in section 7.5. The investigator will also be asked to assess the possible relationship between the AE and the investigational medication as well as any concomitant medications.

#### **7.5 Seriousness (Gravity) – Serious Adverse Events (SAE)**

Each AE is to be classified by the investigator as SERIOUS or NONSERIOUS. This classification of the gravity of the event determines the reporting procedures to be followed.

A **SERIOUS adverse event (SAE)** is an AE that meets one or more of the following criteria/outcomes:

- Death
- Life-threatening (i.e., immediate risk of death)
- In-subject hospitalization or prolongation of existing hospitalization
- Persistent or significant disability/incapacity (any sight-threatening event with ophthalmic products is a significant incapacity)

- Permanent impairment of function or permanent damage to a body structure or requires intervention to prevent permanent impairment or damage
- Congenital anomaly/birth defect
- Any other AE that the investigator or company judges to be serious or which is defined as serious by the regulatory agency in the country in which the AE occurred.

**Note that in view of this trial:**

- **Pregnancy losses where the fetus shows no gross visual evidence of congenital anomalies (when available), will not be reported as a SAE, unless considered to be related to the investigational product.**
- **Admission to hospital for the purpose of term spontaneous vaginal delivery and/or elective caesarean section will not be reported as an SAE.**

**Exposure In Utero**

If the outcome of the pregnancy meets the criteria for immediate classification as a SAE (i.e., congenital anomaly [including that in an aborted fetus]), the investigator is to follow the procedures for reporting SAEs; i.e., **report the event to the APPLE Multicentre Trial Office in Ottawa Canada by fax and follow up by submission of appropriate case report forms and source documentation.**

Additional information regarding pregnancy outcomes that are classified as SAEs follows:

- "Spontaneous abortion" includes miscarriage and missed abortion, if considered to be related to the investigational product (i.e. congenital anomaly)
- All neonatal deaths that occur within one month of birth are to be reported, without regard to causality, as SAEs. In addition, any infant death after one month that the investigator assesses as possibly related to the *in utero* exposure to the investigational medication are also to be reported.
- The "normality" of an aborted foetus can be assessed by gross visual inspection unless there are preabortion laboratory findings suggestive of a congenital anomaly.

**7.6 Reporting of SAEs**

**If a SAE occurs, the APPLE Multicentre Trial office, Ottawa Canada is to be notified within 24 hours of awareness of the event by the investigator. The SAE report form should be sent to the multicentre coordinator and Principal Investigator as outlined in the APPLE Pilot Resource Manual.**

In turn, the Principal Investigator will:

- Review all SAEs and comment via email within 24 hours should clarification be required, and
- If the SAE is related or probably related, and unexpected, the principal investigator will report the SAE to Health Canada using the CIOMS form and notify the REB board of record, Ottawa Health Science Network REB (OHSN-REB) through Clinical Trials Ontario (CTO), as appropriate. Participating sites are responsible for informing their institutions of the event according to their local standard operating procedures.

The initial report is to be followed by submission of more detailed SAE information on the SAE form within 15 working days of the event.

Table 1 REPORTING REQUIREMENTS FOR ADVERSE EVENTS		
Gravity	Reporting Time	Type of Report
SERIOUS (life-threatening or death)	Within 24 hours	Initial report on SAE
	Within 7 days	Final report on SAE
SERIOUS	Within 24 hours	Initial report on SAE
	Within 15 days	Final report on SAE
NON-SERIOUS	Following each of these subject visits: - 20 ± 4 weeks gestational age - Labour & delivery - 6-12 weeks postpartum	Adverse Event CRFs

**NOTE:** In the rare event that the investigator does not become aware of the occurrence of a SAE immediately (e.g., if a trial subject initially seeks treatment elsewhere), the investigator is to report the event within 24 hours after learning of it and document his/her first awareness of the SAE.

All SAEs are to be reported to and reviewed by the Data Safety Monitoring Board (DSMB) according to the DSMB Terms of Reference.

## **7.7 Follow-Up of Adverse Event**

All AEs are to be followed until they are resolved or the subject's participation in the trial ends (i.e., until a final report is completed for that subject).

In addition, all SAEs and those non serious events assessed by the investigator as possibly related to the investigational medication/product are to continue to be followed even after the subject's participation in the trial is over. Such events are to be followed until they resolve or until the investigator assesses them as "chronic" or "stable." Resolution of such events is to be documented on the appropriate CRF.

## **8. STATISTICS**

### **8.1 Statistical and Analytical Plans**

#### 8.1.1 Analysis of Baseline Characteristics

Descriptive statistics will be used to examine the baseline characteristics of excluded subjects and those in the experimental and standard of care arm. Standard deviations will be reported for all characteristics expressed as continuous variables. Medians and ranges will be presented for discrete data.

#### **8.1.2. Pilot Trial Primary Analysis**

The primary analysis will involve a simple estimate of the mean monthly recruitment rate per site along with the 95% confidence interval of the mean.

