### **Pilot Trial Endpoints**

The primary feasibility outcome is the mean recruitment rate per center per month, calculated over 24 months. The secondary feasibility outcomes are: (defined in section 2.2)

1. Proportion of sites requiring >18 months to obtain all required approvals/contracts from time of delivery of all study documents
2. Proportion of screened patients who meet eligibility criteria
3. Proportion of eligible subjects who provide consent
4. Proportion of withdrawals/loss to follow-up among randomized patients
5. Proportion of subject crossover between study arms
6. Rate of compliance with antepartum LMWH use
7. Reasons for physician and patient non-consent

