### **Number of Subjects**

The goal recruitment rate is recruitment of 1 subject every 2 months per centre, or a total of 24 patients in 24 months. The primary endpoint is the mean recruitment rate per month.

---

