## **2. TRIAL OBJECTIVES**

### **2.1 Trial Purpose**

The purpose of this pilot trial is to determine the feasibility of conducting a multicenter randomized trial evaluating antepartum prophylaxis with ASA versus LMWH/ASA in women with confirmed APS and a history of late or recurrent early pregnancy loss.

Given the large sample size needed to adequately power a large multicenter trial that assesses the efficacy of ASA alone versus LMWH/ASA (section 8.2), we first need to determine if we can meet minimum recruitment rates needed for a full multicenter trial to be possible. To test this, we will open the trial at 2 centers with the goal of recruiting one patient every two months. The randomization design for the pilot feasibility trial is the same as the full trial, to best represent what actual recruitment rates and trial conditions would be like in the full trial. If the pilot feasibility trial is successful, then the secondary outcomes collected will be used in the analysis of the larger full multicenter trial.

The purpose of the full trial will be to determine the efficacy and safety of antepartum prophylaxis with aspirin alone to improve the live birth rate in women with confirmed APS and a history of late or recurrent early pregnancy loss, compared to the standard of care regime of LMWH/ASA prophylaxis.

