### **2.3 Pilot Trial Endpoints**

The primary feasibility outcome of the pilot trial is a mean recruitment rate of 0.5 subjects per center per month. The secondary feasibility outcomes of the pilot trial and associated *a priori* feasibility targets are as follows:

1. Proportion of sites requiring >18 months to obtain all required approvals/contracts from time of delivery of all study documents: <50%.
2. Proportion of screened patients who meet eligibility criteria (i.e. patients who meet inclusion criteria and are also eligible based on exclusion criteria): >30% of subjects
3. Proportion of eligible subjects who provide consent: >30% of subjects
4. Proportion of withdrawals/loss to follow-up among randomized patients: <10% of subjects
5. Crossover rate between standard of care and experimental study arms: <20%
6. Level of compliance with study drug: >80% compliance rate of total antepartum LMWH use
7. Reasons for physician and patient non-consent

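### The confidence interval for the primary recruitment rate has no stated unit of replication and no count-based method; with two centres, an exact Poisson interval on the total count would be sounder

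*Combined protocol and SAP*

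**What the plan says.** The Pilot Trial Endpoints part of the synopsis defines the primary outcome as "the mean recruitment rate per center per month, calculated over 24 months". Section 2.3 sets the target as "a mean recruitment rate of 0.5 subjects per center per month". Section 2.1 says "we will open the trial at 2 centers", and the synopsis under Number of Subjects translates the goal into "recruitment of 1 subject every 2 months per centre, or a total of 24 patients in 24 months". The same synopsis paragraph then names the primary endpoint as a mean rate per month, without mentioning the centre.

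The whole primary analysis is the single sentence in section 8.1.2: "a simple estimate of the mean monthly recruitment rate per site along with the 95% confidence interval of the mean". It gives no unit of replication, no denominator and no interval formula. By contrast, section 8.1.3 names Wilson's score method for the secondary proportions.

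**The concern.** The outcome is a count of women over centre-time. The sentence in 8.1.2 treats it as an ordinary mean and leaves open what is being averaged. The same data can therefore give very different intervals, and nothing written in advance fixes which one is reported. One available reading, across centres, has two observations. Its width then depends on how far the two centres differ and hardly at all on how many women were recruited. The other natural reading, across months, gives a symmetric interval for a skewed count, which is least reliable when recruitment is poor, and that is the situation the pilot is meant to detect. This interval is the only stated measure of uncertainty on the primary outcome.

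**Working it through.** **Inputs.** Two centres (2.1, 3.1); 24 months (synopsis, 2.2); target 0.5 per centre per month (2.3); 95% level (8.1.2). Assumptions: both centres are open for all 24 months, and counts are Poisson where a probability is given.

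**The plan's own figure.** 2 centres × 24 months × 0.5 = 24 women, as in section 8.2. The documents give no interval for the rate, so there is none to reproduce.

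**Reading A: the two centre rates are the replicates.** With counts a and b, the mean is (a + b)/48. The standard error is |a − b|/48, and t(0.975, 1 df) = 12.706, so the half-width is 12.706 × |a − b|/48.

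| Split | Mean | 95% interval |
|---|---|---|
| 12/12 | 0.50 | 0.50 to 0.50 |
| 13/11 | 0.50 | -0.03 to 1.03 |
| 14/10 | 0.50 | -0.56 to 1.56 |
| 16/8 | 0.50 | -1.62 to 2.62 |
| 13/12 | 0.52 | 0.26 to 0.79 |
| 12/11 | 0.48 | 0.21 to 0.74 |

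When the total is 24, the difference between centres is 0 or at least 2. A difference of 2 already gives a half-width of 12.706 × 2/48 = 0.53, which exceeds the mean of 0.50. So every split of 24 gives zero width or a negative lower limit. If each centre's count is Poisson with mean 12, summing over all pairs gives about 8% with zero width, 70% with a negative lower limit and 22% with neither.

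**Reading B: months are the replicates.** With Poisson variance at a mean of 0.5 and t(0.975, 47 df) = 2.012, 48 centre-months give 0.50 ± 2.012 × √(0.5/48) = 0.295 to 0.705. Using 24 calendar months gives 0.289 to 0.711.

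**Exact Poisson (Garwood).** For k women in T centre-months, the limits are χ²(0.025; 2k)/(2T) and χ²(0.975; 2k + 2)/(2T). For k = 24 the count limits are 15.38 and 35.71; divided by 48 they are 0.320 and 0.744, whatever the split.

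**Reading B when recruitment falls short.** The normal interval is k/48 ± 1.96 × √k/48.

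- 16 women: 0.333 ± 1.96 × 4/48 = 0.170 to 0.497, which excludes 0.5. Exact Poisson is 0.191 to 0.541, which includes it.
- That exclusion is narrow: with the t multiplier the upper limit is 0.333 + 2.012 × 4/48 = 0.501. With 15 women the multiplier no longer matters: the upper limits are 0.3125 + 1.96 × 3.873/48 = 0.471 and 0.3125 + 2.012 × 3.873/48 = 0.475, while exact Poisson gives 24.74/48 = 0.515.
- 12 women: normal 0.109 to 0.391, exact Poisson 0.129 to 0.437. Both exclude 0.5.

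In simulation with Poisson counts in 48 centre-months, the upper limit of the t interval falls below the true rate in about 4.7% of trials at 0.5 per month and about 7.2% at 0.25. The nominal figure is 2.5%, and exact Poisson gives about 2% in both cases.

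**The case against.** The strongest reply is that 8.1.2 does not make the centres the replicates. The synopsis speaks of a rate calculated over 24 months and of a mean per month, so averaging over months is at least as natural. At the planned count that reading gives about 0.30 to 0.70, close to the exact Poisson 0.32 to 0.74. This stands. A reader might infer that the plan commits the trial to an impossible or zero-width interval; the text does not support that. Even across centres the failure is not certain, since 13/12 gives a usable interval, and the figures above assume a t multiplier that the plan does not name.

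It can also be said that an exact Poisson interval is itself an interval for a mean count, so the present wording does not rule it out. That is true, but nor does it select it.

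A third objection is that exact Poisson ignores variation between centres. This stands as a limit on the remedy. In simulation, its coverage of the mean rate in a wider population of centres is about 96% with no between-centre variation, 88% at a coefficient of variation of 0.25 and 70% at 0.5 (the two coefficients are assumptions). Listing each centre's rate discloses the problem but does not cure it.

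**Conclusion.** The point holds as a cheap improvement. The primary interval is under-specified. The across-centre reading breaks down for every split of the planned 24. The month-based reading is adequate near 24, but its upper limit is too low when recruitment falls short, with roughly two to three times the nominal upper-tail error in the two cases simulated. These sizes rest on Poisson counts and on 48 open centre-months.

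A reader might go further and infer that the interval decides whether the 828-participant trial proceeds. The documents do not say so. Sections 2.3 and 8.2 set the target as a point value, and with equal centre-time the point estimate is the same under every method. What is gained is a valid, pre-specified statement of uncertainty on the primary outcome.

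**What to change.** Replace the sentence in 8.1.2 with wording such as: *The recruitment rate is the total number of women randomised divided by the total observed open centre-months, with an exact (Garwood) Poisson 95% confidence interval. Each centre's count, open months and rate are shown descriptively, and the interval applies to these two centres only.*

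Open months should be the denominator because section 2.3 itself allows for centres needing more than 18 months for approvals; the 48 centre-months used above are the maximum.

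The cost is one sentence, with no change to design, data collection or patient care. The drawback is the assumption of a common, constant rate: the interval does not capture between-centre variation and should not be extended to the 40 centres planned in section 8.2. Other count-based methods would also be acceptable if named in advance.

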#### **8.1.3. Pilot Trial Secondary Analyses**

Proportions with 95% confidence intervals will be calculated using Wilson's score method for the following secondary analyses: 1) proportion of screened subjects who meet eligibility criteria, 2) proportion of eligible subjects who provide consent, 3) proportion of withdrawals/losses to follow-up among randomized subjects, 4) proportion of sites requiring >18 months to obtain all required approvals/contracts from time of delivery of all study documents, and 5) proportion of crossover between study arms. Reasons for non-consent will be collected and analyzed using qualitative thematic analysis.

#### **8.1.4. Full Trial Analyses**

Several secondary outcomes will be collected in the pilot trial, which will be included in the analysis of the full trial if there are no significant changes to the trial design.

**Primary analysis:** Analysis will be performed by intention to treat. Intention to treat analysis will be supplemented by a sensitivity analysis that excludes subjects who did not complete the allocated treatment plan. The live birth rate will be compared in the experimental and standard of care arm by an unadjusted Fisher's test of proportions, with 95% confidence intervals provided.

**Secondary analysis:** Analysis will be performed by intention to treat. Intention to treat analysis will be supplemented by a sensitivity analysis that excludes subjects who did not complete the allocated treatment plan. Proportions will be compared between study arms by an unadjusted Fisher's test, with 95% confidence intervals reported. The following outcomes will be analyzed: Pregnancy loss by central laboratory testing, pregnancy loss by gestational age (<10 weeks, 10-19 weeks,  $\geq$ 20 weeks gestation), pre-eclampsia, early onset pre-eclampsia, severe pre-eclampsia, SGA <10th percentile, SGA <5th percentile, SGA <3rd percentile, placental abruption requiring delivery, pre-term delivery <37 weeks gestation, symptomatic VTE, symptomatic ATE, major bleeding, clinically relevant non-major bleeding, non-major non-CRNMB, major peripartum bleeding, minor peripartum bleeding, HIT, symptomatic fracture, allergic reaction, and all-cause mortality.

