In contrast, two subsequent trials evaluated LMWH/ASA versus ASA alone found no difference in live birth rates. Farquharson et al. randomized 98 women with at least 3 consecutive pregnancy losses or 2 pregnancy losses with proven fetal death after 10 weeks gestation with persistently positive lupus anticoagulant and/or anticardiolipin antibodies at least 6 weeks apart. Women were randomized to antepartum LMWH/ASA versus ASA alone until delivery. There was no difference in live birth rate between treatment arms (78% versus 72%, p=0.49). One limitation to this study is a 25% reported crossover rate between study arms, based on physician or patient preference. Lastly, Laskin et al. completed a randomized trial of women a history of 2 or more pregnancy losses, including patients with one of: ANA positivity, lupus anticoagulant or anticardiolipin antibodies, or inherited thrombophilia, randomizing participants to LMWH/ASA versus ASA alone during pregnancy. Of the subgroup with lupus anticoagulant or anticardiolipin antibody positivity, there was no difference in the live birth rate (77% versus 75%) among 42 patients. Laskin et al. conclude “these findings contribute to the growing body of literature that contests the emerging standard of care comprising LMWH/ASA”. Limitations to these negative studies include a 25% crossover rate between study arms, small sample size and

varying definitions of APS. Furthermore, no trial has evaluated prophylaxis in women with pregnancy loss and persistent anti-β2 glycoprotein antibodies. Given the poor quality evidence and mixed results for the use of LMWH/ASA prophylaxis in this setting, a large randomized trial is still needed.

When uncertainty exists in pregnancy, health care providers and patients often err on the side of treatment in hopes of preventing complications. Our goal is to minimize uncertainty, to provide clear recommendation to women with APS and pregnancy loss based on high-quality evidence. The full APPLE trial will compare the live birth rates in women assigned to the standard of care arm, prophylactic LMWH and ASA, compared to the experimental arm, ASA alone.

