### **1.3 What are the risks with the standard of care regime of prophylactic LMWH/ASA?**

Downsides of LMWH include burden of injections (up to 400 injections/pregnancy), cost (\$4,000/pregnancy) and side effects of LMWH. In a systematic review of LMWH use in pregnancy, the most common side effects were bleeding (1.98%) which included significant antepartum bleeding, postpartum hemorrhage, and abdominal hematomas. Allergic skin reactions (1.8%) were also reported, some of which may be associated with HIT antibodies. Being on heparin lowers the likelihood that a woman receives epidural analgesia at the time of delivery, given the documented risk of epidural hematoma and associated hemiplegia when LMWH is not held prior to epidural analgesia. Serious and life-threatening complications of LMWH are rare, but possible. HIT has rarely been reported in pregnancy with the use of LMWH. The risk of osteoporosis and symptomatic fracture is rare, and significantly lower compared to unfractionated heparin.

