**Allergic reaction**

A reaction following the administration of LMWH that results in anaphylaxis or a rash requiring discontinuation of the allocated LMWH.

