### **3.6 End of Study**

Study crossover, compliance, and early termination will be documented. Reasons for study crossover (patient or physician preference) will be documented. If a subject terminates the study early, ASA and/or LMWH will be left to the treating physician, and documented. Primary and secondary outcomes will be captured.

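### Full-trial harm outcomes are analysed by allocated arm and then among completers only; neither analysis counts harm by the LMWH actually received, and the second may remove the women who were harmed

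*Combined protocol and SAP*

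**What the plan says.** Section 8.1.4 (Full Trial Analyses, secondary analysis) sets one rule for efficacy and harm outcomes alike: "Analysis will be performed by intention to treat". The next sentence adds: "Intention to treat analysis will be supplemented by a sensitivity analysis that excludes subjects who did not complete the allocated treatment plan". The outcomes covered include every bleeding category, HIT, symptomatic fracture and allergic reaction. Arms are compared by an unadjusted Fisher's test. The section does not say what counts as not completing the plan.

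Other sections bear on this:

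- Section 2.3 gives a pilot feasibility target: "Crossover rate between standard of care and experimental study arms: <20" per cent.
- Section 1.1 says of an earlier trial of the same comparison: "One limitation to this study is a 25% reported crossover rate between study arms, based on physician or patient preference".
- Section 4.3 stops study drug at listed outcome events, among them major bleeding, a platelet count below 50 x 10^9/L and symptomatic fracture. It also says that safety data from every subject will be analysed, but names no grouping.
- Section 2.6 defines allergic reaction as: "A reaction following the administration of LMWH that results in anaphylaxis or a rash requiring discontinuation of the allocated LMWH".
- Section 3.6 states: "Study crossover, compliance, and early termination will be documented". The Schedule of Mandatory Events and sections 3.3, 6.4 and 6.5 add drug regime, a medication diary and compliance.

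**The concern.** Avoiding LMWH harm is part of the case for the trial (section 1.3), and section 2.4 promises safety reporting. Under intention to treat, a woman allocated to ASA who takes LMWH and bleeds is counted under ASA. A woman allocated to LMWH who does not take it lowers the LMWH rate. Both pull the arms together. The usual partner to such an analysis is one by treatment received, and the plan has none.

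The supplementary analysis it does have selects on completion. For several harms, stopping the drug is a consequence of the event, or part of its definition. Both planned analyses could therefore understate the harm of LMWH, for different reasons.

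**Working it through.** **1. The plan's own sample size (section 8.2).** Inputs given: 60% in the ASA arm, a 10-point difference, 80% power, alpha 0.05, 10% drop-out. Assumed: 70% in the LMWH/ASA arm, a two-sided test and 1:1 allocation.

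n = [1.96 x sqrt(2 x 0.65 x 0.35) + 0.84 x sqrt(0.24 + 0.21)]^2 / 0.10^2 = 356 per arm.

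With continuity correction, (356/4) x [1 + sqrt(1 + 4/(356 x 0.10))]^2 = 376 per arm, or 752 in all. Then 752 x 1.1 = 827.2, rounded up to 828. The stated figure is reproduced. It gives 828/2 = 414 randomised per arm, or about 372 after 10% drop-out.

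**2. Dilution under intention to treat.** Let pL and pA be the event risks on LMWH/ASA and on ASA, and cL and cA the crossover shares in the two arms. If crossovers take on the full risk of the other treatment:

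[pL(1 - cL) + pA cL] - [pA(1 - cA) + pL cA] = (pL - pA)(1 - cL - cA).

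The only bleeding figure in the documents is 1.98% in LMWH users (section 1.3), with no comparator. As an assumption, take it as the excess due to LMWH. The background rate is also not given, so power is shown for backgrounds of 0 and 1.98% (normal approximation, 414 per arm).

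| Crossover | Share retained | Difference, points | Power, background 0 | Power, background 1.98% |
|---|---|---|---|---|
| none | 100% | 1.98 | 82% | 39% |
| 10% in each arm | 80% | 1.58 | 63% | 27% |
| 20%, LMWH arm only | 80% | 1.58 | 73% | 28% |
| 20%, ASA arm only | 80% | 1.58 | 56% | 26% |
| 20% in both arms | 60% | 1.19 | 41% | 17% |

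Section 1.3 also says: "Allergic skin reactions (1.8%) were also reported". Treated in the same way, 1.8 points becomes 1.44 (20% in one arm) or 1.08 (20% in both).

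**3. What the completers-only analysis does.** Two groups matter.

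- ASA-arm women who took LMWH. If crossing over counts as non-completion, they are excluded. That removes their dilution of the ASA arm, but also discards their experience on LMWH.
- Women whose drug was stopped because of the harm. Suppose a share f of women with the event is excluded for that reason. The rate among those kept is p(1 - f)/(1 - pf). With p = 1.98% as an illustration and f = 0.5, this is 0.99/(1 - 0.0099) = 1.00%. With f = 1 it is zero. If f is the same in both arms, the difference shrinks by nearly the factor (1 - f).

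The documents do not fix f. It depends on the missing definition of completion and on how many events fall before the plan ends. The mechanism applies to major bleeding, thrombocytopenia and fracture (section 4.3) and to the rash form of allergic reaction (section 2.6). Clinically relevant non-major bleeding is not on the stopping list.

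**4. The pilot.** With about 12 women per arm, 12 x 0.0198 = 0.24 bleeds are expected in the LMWH arm. No analysis choice matters at that size.

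**The case against.** Section 1.7 describes a pragmatic design that asks what happens when LMWH is removed. Comparing allocated strategies answers that question, so intention to treat is a proper main analysis. That stands, and the fix keeps it.

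A reader might infer that harms are compared only by intention to treat. The documents do not support this: the sentence after the quoted one plans a second analysis of the same outcomes. The gap is that this second analysis is the wrong kind for harms. A reader might also infer that the full trial accepts 20% crossover. Section 2.3 gives a pilot feasibility target of less than 20%, not an assumption of the full-trial analysis. The 25% belongs to an earlier trial and would miss that target.

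Power for harms is limited mainly by rarity. By exact Fisher test at 372 per arm with no crossover, LMWH at 1.98% against ASA at 1% gives 12% power. Larger assumed effects show steeper losses: 5% against 2% gives 55% power with no crossover, 26% with 16.7% crossing in each arm and 15% with 25%. But 5% is well above the only documented rate. The formula also overstates dilution from late or partial switching. These points stand, so the finding rests on bias and not on a particular power figure.

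An analysis by treatment received has its own faults. Exposure follows patient or physician preference and starts at different times. LMWH is due to stop at 37 weeks or labour onset (section 3.4), and it may be given at the physician's discretion after an endpoint (section 4.3). A crude rule of one dose and any later event would misattribute bleeding. This stands and shapes the fix.

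Investigator causality assessment (section 7.4) and DSMB review of serious events (section 7.6) give some protection, but neither is a comparison between treatments.

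**Conclusion.** The concern holds for the full-trial analysis of harms. Intention to treat keeps about 80% of an LMWH harm difference with 20% crossover in one arm, or 10% in each, and about 60% with 20% in both. This assumes that crossovers carry the full risk of the other treatment. The planned sensitivity analysis does not restore the difference. It excludes ASA-arm women exposed to LMWH if they are classed as non-completers, and on one reading of an undefined term it excludes women because they had the event.

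The background bleeding rate, the split of crossover between arms and the share of harmed women excluded are not in the documents, so the size is a range. The effect on the pilot is negligible. However, section 8.1.4 carries pilot outcomes into the full analysis if the design does not change significantly, so the rules are best fixed before outcomes are known.

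**What to change.** 1. Keep the intention-to-treat comparison of all harm outcomes.
2. Define non-completion of the allocated plan, and state that in the harm analyses stopping because of a harm event does not count as non-completion.
3. Add a supportive, non-randomised safety analysis by antepartum prophylactic LMWH actually received, for the bleeding outcomes, HIT, fracture and allergic reaction:
   - count events from the first LMWH dose to a pre-specified window after the last dose;
   - express events per exposed time, or otherwise account for differing starts of exposure;
   - report peripartum bleeding separately;
   - do not count LMWH started after a study endpoint, such as VTE, as prophylaxis exposure.

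The cost is some wording in section 8.1.4 and one further set of tables. Drug regime, diary, compliance and crossover are already recorded. The sponsor should check that the case report form gives usable first and last dose dates in both arms. The downside is confounding by patient and physician preference, so the added analysis should be labelled supportive and read only beside intention to treat.
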